### 4 Introduction

The majority of depressed patients do not achieve remission with current methods. A common and disabling symptom after treatment is anhedonia — the inability to fell pleasure and reduced "drive". Today, there is no specific and effective treatment method for anhedonia. Pramipexole is a dopamine agonist used in Parkinson's disease and has been shown in several clinical studies to be effective against anhedonia symptoms in this disease. Clinical experience has shown a treatment effect with high-dose pramipexole in treatment-refractory depression, but randomized clinical studies have only been conducted with low-dose pramipexole and have not investigated the specific effects against anhedonia. In a recently completed pilot study from our research group, approximately one third of patients showed a treatment effect on high dose pramipexole.

The purpose of this study is to investigate the effect of add-on pramipexole on anhedonia depression and other symptoms in patients with depressive disorders.

The SAP covers the primary and some of the secondary efficacy variables.

For detailed information, see the Protocol which has been pre-published (1)

# 5 Objectives and issues

The overall objective is to investigate the efficacy and tolerability of add-on pramipexole in anhedonia depression.

Biomarkers have been collected for a subset of the patients to demonstrate target engagement and find treatment predictors.

# 6 Study design

#### 6.1 Study design

This is a double-blind trial in which a total of 80 patients are randomized to receive either add-on pramipexole or placebo for nine weeks. Study participants undergo optional fMRI examination and lumbar puncture at baseline and at the end of the RCT.

For detailed information, see the pre-published Protocol (1).

## 6.2 Sample size calculation

For the primary question (SHAPS), a linear mixed model with repeated measures (w 3, w 6 and w 9) will be used, where the primary question will be answered with the overall comparison between the

randomized groups. Any group differences at baseline are corrected by including the baseline values as a covariate in the model. The estimated effect size of pramipexole treatment is estimated at 0.27 as this has been reported in other studies of antidepressant drugs. This corresponds to a score difference in MADRS of approximately 4 points which is considered a clear clinical improvement and corresponds to  $\geq$  4 points on SHAPS. Estimate of the correlation coefficient between repeated measures of MADRS scores is based on material from our previous pilot study (r=0.5). In a power calculation with strength of 80% and  $\alpha$ =0.05, 74 research subjects were estimated to be needed. In the original power calculation, the number of dropouts was estimated to be less than 5% (based on the pilot study), whereby we needed to include 80 research subjects in the study (ITT)

After a planned interim analysis, conducted by an external statistician, we estimate that we need to include 80 patients who reach the week 9 visit (end of study).

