### 8 Outcome measures

### 8.1 Primary efficacy outcome measures

The primary efficacy outcome measure is the absolute change in the SHAPS (2) between baseline and week 9.

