### 10.2 Effect

### 10.2.1 Primary

To answer the primary question, a linear mixed model with repeated measures is used with severity of anhedonia symptoms (SHAPS total score) as the dependent variable and time (week), treatment (pramipexole or placebo), and the interaction of time by treatment as independent variables. The

SHAPS total score at baseline will be used as a covariate in the model. In the event of missing measurements at different time points, this will be compensated for with last observation carried forward (LOCF). Normal distribution is expected based on previous studies.

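### Section 6.2 decides the primary question on the average over weeks 3, 6 and 9, section 8.1 defines the outcome at week 9 only, and section 10.2.1 names no deciding contrast

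*SAP*

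**What the plan says.** Three sections of the SAP bear on the primary test.

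- **6.2 Sample size calculation** says that "a linear mixed model with repeated measures (w 3, w 6 and w 9) will be used" for SHAPS and that "the primary question will be answered with the overall comparison between the" randomised groups, with baseline as a covariate. It gives the planning value: "The estimated effect size of pramipexole treatment is estimated at 0.27". After the interim analysis it sets the target by week-9 attendance: "we need to include 80 patients who reach the week 9 visit".
- **8.1 Primary efficacy outcome measures** says: "The primary efficacy outcome measure is the absolute change in the SHAPS (2) between baseline and week 9".
- **10.2.1 Primary** takes "severity of anhedonia symptoms (SHAPS total score) as the dependent variable" and uses "time (week), treatment (pramipexole or placebo), and the interaction of time by treatment as independent variables", plus baseline SHAPS. It does not say which term or contrast decides, or whether week enters as a factor or as a number.

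No other section reconciles these statements. Section 10.2.2 applies the same model to secondary outcomes with more than two measurement points, so the gap carries over to them.

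**The concern.** The conflict is about visits. Section 6.2 combines three; section 8.1 names one. Modelling the score instead of the change is not a problem, because with baseline as a covariate the group contrast is the same for both.

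Section 10.2.1 cannot settle the matter by itself. Once a time-by-treatment interaction is in the model, the meaning of the treatment coefficient depends on coding. With dummy-coded weeks it is the difference at the reference week. With uncentred numeric week it is the difference extrapolated to week 0. The three-visit average has to be requested as a contrast.

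The two quantities coincide only if the effect is the same at all three visits, and even then the tests have different precision. Someone who follows 8.1 and someone who follows 6.2 can therefore report different estimates and different significance results from the same data.

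**Working it through.** **Inputs from the SAP:** effect size 0.27, r = 0.5 between repeated MADRS scores, three visits, 80% power, N = 74, and a later target of 80 patients reaching week 9 (all 6.2); two-sided 0.05 (10.1).

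**Assumptions not in the SAP:** 0.27 is Cohen's f, so the standardised difference is 2 × 0.27 = 0.54; 1:1 allocation; compound symmetry; r = 0.5 also holds for SHAPS; complete data, so no LOCF. The baseline-to-follow-up correlation rb is not given. I show no covariate gain and rb = 0.5.

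**Step 1: reproduce N = 74.** For the overall between-groups effect, the noncentrality is λ = f²·N·m / (1 + (m − 1)r), with 1 and N − 2 degrees of freedom.

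- Overall, m = 3: 0.27² × 74 × 3 / 2 = 8.09, power 80.1%. The smallest even N for 80% is 74.
- Week 9 alone, m = 1: 0.27² × 74 = 5.39, power 63.0%. The smallest even N is 110.

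Other readings do not give 74: two visits give 84, four give 70, the interaction gives 24, and 0.27 read as a standardised difference gives 288 (normal approximation). So 74 fits the comparison in 6.2. That is evidence of intent and no proof: a week-9 test with rb of about 0.58 would also need 74.

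**Step 2: power at N = 80.** For effect δ, λ = δ²·N / (4V). V is (1 + 2r)/3 − rb² for the average and 1 − rb² for week 9. Degrees of freedom are N − 2, or N − 3 with the covariate.

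- No covariate gain: V = 2/3 = 0.667 (average) and 1 (week 9).
- rb = 0.5: V = 0.667 − 0.25 = 0.417 and 1 − 0.25 = 0.75.

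Example, constant effect, no gain: λ = 0.54² × 80 / (4 × 0.667) = 8.75 overall and 0.54² × 80 / 4 = 5.83 at week 9.

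**Step 3: disagreement.** Disagreement means that one test has p < 0.05 and the other does not. The two test statistics are treated as bivariate normal with means √λ and correlation √(V average / V week 9): √(0.667/1) = 0.816 with no gain, √(0.417/0.75) = 0.745 at rb = 0.5.

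Linear build-up means effects in the ratio 1/3, 2/3, 1, so the average is two-thirds of the week-9 effect. The result depends on where 0.54 is placed. At week 9, the average is 0.54 × 2/3 = 0.36. On the average, week 9 is 0.54 × 3/2 = 0.81.

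| Effect pattern | rb | Power overall / week 9 | Disagreement |
|---|---|---|---|
| Constant 0.54 | none | 83% / 66% | about 20% |
| Constant 0.54 | 0.5 | 96% / 79% | about 18% |
| Linear, 0.54 at week 9 | none | 50% / 66% | 24% |
| Linear, 0.54 at week 9 | 0.5 | 69% / 79% | 20% |
| Linear, 0.54 on average | none | 83% / 95% | 12% |
| Linear, 0.54 on average | 0.5 | 96% / 98.5% | 4% |

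The overall test has more power under a constant effect. Week 9 has more under both linear patterns shown. Neither choice is safely the conservative one.

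**The case against.** The strongest reply is that the rule exists. Section 6.2 says how the primary question will be answered, 10.2.1 fits a model that can deliver that comparison and names no competing contrast, and 8.1 sits under outcome measures and prescribes no test. The reproduction of 74 points the same way. This stands as far as it goes: it makes 6.2 the better reading and lowers the severity. It does not remove the mismatch, because an outcome fixed at week 9 is not what a three-visit average estimates, and the recruitment target is also counted at week 9.

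A second reply is that the figures rest on assumptions the SAP does not make. That is correct. Cohen's f, equal allocation, compound symmetry, rb and the time course are all supplied here, and r comes from MADRS. The linear figures also change sharply with where 0.54 is placed. Since 6.2 appears to power the overall comparison, placing it on the average is at least as natural as placing it at week 9.

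A third is that LOCF makes some week-9 values copies of earlier ones. That would pull the two contrasts together, by an amount not quantified here.

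A reader might go further and infer that the plan has an inflated type I error. If the contrast were picked after unblinding and either test could be claimed, the error would be about 7% to 9%. Nothing in the SAP says the choice will be made that way, so this bounds a misuse and does not describe the plan.

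**Conclusion.** The inconsistency is real and should be fixed. Sections 6.2 and 8.1 point to different primary quantities, and 10.2.1 does not say which one decides. Under the assumptions listed, disagreement on significance at N = 80 is about 18% to 20% for a constant effect. For linear build-up it is 20% to 24% or 4% to 12%, depending on where the effect is placed. These are illustrations over assumed patterns and do not bound what could happen.

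Two stronger readings are not supported. One is that the SAP leaves the primary test undefined: 6.2 does define it, in a place where it is easily missed. The other is that the trial is underpowered: the 63.0% applies only if week 9 decides, 0.54 is the week-9 effect and baseline adjustment gains nothing. The sample size fits the comparison that 6.2 names.

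**What to change.** Before the randomisation code is broken, state in 10.2.1 that the primary test is the model-based treatment difference in SHAPS total score averaged over weeks 3, 6 and 9, with week as a categorical factor, two-sided at 0.05. Reword 8.1 to match. Report the week-9 difference and the time-by-treatment interaction as supportive. Section 10.2.2 then inherits the same contrast.

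The cost is wording only: no new data and no change in sample size. The downside is that the average is smaller than the week-9 difference if the effect builds up over time. Under linear growth to 4 points at week 9, for example, it is 4 × 2/3 = 2.7 points.

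If the sponsor prefers week 9 as primary, 6.2 must be amended and its power restated for that contrast. With 0.54 at week 9, 80% power needs 110 patients without covariate gain, or 84 at rb = 0.5. For the average under a constant effect, the figures are 74 and 48.

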#### 6.3 Randomization

The randomization process uses a randomization list generated by an independent statistician at Clinical Studies Sweden – Forum South. Blinded study personnel are unaware of the randomization outcome. Research participants are included/randomized consecutively as they are deemed eligible for the study.

#### 6.4 Interim analysis

An interim analysis was planned according to the original protocol. In June of 2024 an independent statistician conducted an interim analysis on the primary outcome and number of dropouts. The result of this interim analysis was that we decided to increase the number of recruited patients to 80 with complete efficacy data through the week 9 visit.

### 8 Outcome measures

### 8.1 Primary efficacy outcome measures

The primary efficacy outcome measure is the absolute change in the SHAPS (2) between baseline and week 9.

# 8.2 Secondary efficacy outcome measures

The secondary efficacy outcome measure are

- Core depression symptoms (HDRS-6 (3))
- Anhedonia (DARS (4), covering additional anhedonia domains compared to the SHAPS)
- General depressive symptoms (MADRS-S (5))
- Sleep disturbances (ISI (6))
- Apathy symptoms (AES (7))
- Anxiety symptoms (GAD-7 (8))
- Quality of life (BBQ (9))

#### 8.3 Additional outcomes measures

#### Additional outcomes are

- accelerometry
- fMRI

### 8.4 Safety outcome measure

#### Adverse events

# 9 Data processing

### 9.1 Missing values

If clinical efficacy measurement values are missing at different times, this will be compensated for with last-observation-carried-forward (LOCF).

For the mechanistic secondary outcomes (e.g. fMRI), analyses will be performed only on those subjects who have the necessary data available for these specific analyses, meaning that no imputation will be applied.

#### 9.2 Calculated variables

Total score of the SHAPS will be calculated by summarizing each item with a value from 1 to 4 (max score 56). Total score on the other rating scales will be calculated according to the instructions for each scale.

#### 9.3 Transformations

If assumptions regarding normal distribution are not met, variables may be transformed.

# 10 Statistical analysis

#### 10.1 Statistical basis

Descriptive statistics will be given as mean (SD), median (Q1–Q3) and (Min–Max) for continuous variables. The number of observations will also be given.

The randomization groups will be compared. Two-sided test of statistical significance is to be used, and the chosen significance level is 0.05. No adjustment for multiplicity will be made.

### 10.2 Effect

### 10.2.1 Primary

To answer the primary question, a linear mixed model with repeated measures is used with severity of anhedonia symptoms (SHAPS total score) as the dependent variable and time (week), treatment (pramipexole or placebo), and the interaction of time by treatment as independent variables. The

SHAPS total score at baseline will be used as a covariate in the model. In the event of missing measurements at different time points, this will be compensated for with last observation carried forward (LOCF). Normal distribution is expected based on previous studies.

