10.2.2 Secondary

The same statistical method and model as above is used for the other secondary outcome measures where there are more than two measurement points

In addition to analyzing total scores as continuous variables, we will also do descriptive analyses of treatment response and remission status. For this purpose, we use established cut-offs. Response according to the SHAPS is defined as an improvement of  $\geq 50\%$  on total score (each item rated from 1-4), and remission as a SHAPS score of  $\leq 2$ , based on an alternative scoring approach in which each item is rated either 0 or 1 (10, 11). Initially, the published protocol defined SHAPS remission as a score of  $\leq 3$ . However, to maintain consistency with the original Snaith et al. publication (12) — the basis of our SHAPS inclusion criteria — we've updated the definition to a score of  $\leq 2$ . This was done before all data had been collected and before the randomization code was broken.

Response on the MADRS is defined as ≥50% improvement and remission as a score ≤10. Fisher's Exact test will be used to compare dichotomous outcomes.

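### LOCF is the only stated rule for missing SHAPS scores; the planned mixed model does not need it for patients with a post-baseline score, and it can bias the result

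*SAP*

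**What the plan says.** SAP 10.2.1 specifies a linear mixed model for SHAPS total score with time, treatment, their interaction and baseline SHAPS. It then adds: "In the event of missing measurements at different time points, this will be compensated for with last observation carried forward (LOCF"). Section 9.1 sets the same rule for all clinical efficacy measures: "If clinical efficacy measurement values are missing at different times, this will be compensated for with last-observation-carried-forward (LOCF"). The only other missing-data rule, no imputation, covers mechanistic outcomes such as fMRI. Section 10.2.2 carries the method further: "The same statistical method and model as above is used for the other secondary outcome measures where there are more than two measurement points".

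Two readings of the primary comparison matter for the size of the effect. Section 6.2 lists visits at weeks 3, 6 and 9 and says "the primary question will be answered with the overall comparison between the" randomised groups. Section 8.1 says "The primary efficacy outcome measure is the absolute change in the SHAPS (2) between baseline and week 9".

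On dropout, 6.2 reports that originally "the number of dropouts was estimated to be less than 5% (based on the pilot study"). Section 6.4 says that "an independent statistician conducted an interim analysis on the primary outcome and number of dropouts", after which the target became 80 patients with complete data through week 9. No observed dropout rate is given.

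**The concern.** A repeated-measures mixed model fitted by likelihood takes incomplete records as they are. Every patient with at least one post-baseline score contributes, and the treatment comparison is valid if the scores are missing at random. Filling the gaps by LOCF beforehand replaces that assumption with a stronger one, that a patient's score stays where it was at the last visit. It also enters the copies as if they were measurements.

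Where patients are improving, LOCF understates improvement in whichever arm loses more patients, or loses them earlier or from a steeper course. The bias therefore depends jointly on dropout rate, timing, trajectory and reason for leaving in each arm. Dropout rates alone give neither its size nor its direction. Week 9 is hit hardest, because that is where copied scores accumulate.

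The rule also leaves open whether the baseline score may be carried forward for a patient with no post-baseline score.

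**Working it through.** **Step 1: the plan's own sample size.** Inputs from SAP 6.2: effect size 0.27, three visits, r = 0.5, 80% power, alpha 0.05. Reading 0.27 as Cohen's f (assumption) with equal allocation (assumption), the noncentrality is λ = N·f²·m / (1 + (m − 1)ρ) = 74 × 0.0729 × 3 / 2 = 8.09 on 1 and 72 df. Power is 0.801, so the stated 74 is reproduced. Allowing 5% dropout, 74 / 0.95 gives 78, and 80 covers it. The sample size is not in dispute. The 4-point difference ("This corresponds to a score difference in MADRS of approximately 4 points", which 6.2 equates with at least 4 on SHAPS) then implies SD = 4 / (2 × 0.27) = 7.4.

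**Step 2: what LOCF does to the week 9 difference.** Assumed mean improvement at weeks 3/6/9 is 2/4/6 on placebo and 3.33/6.67/10 on drug, so the true week 9 difference is 4.0. A share s = 0.6 of dropouts leaves after week 3 and the rest after week 6. For dropout p in an arm:

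week 9 mean under LOCF = (1 − p)·m9 + p·s·m3 + p·(1 − s)·m6

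Improvement lost per unit of dropout:
- drug: 10 − 0.6 × 3.33 − 0.4 × 6.67 = 5.33
- placebo: 6 − 0.6 × 2 − 0.4 × 4 = 3.20

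The LOCF difference is therefore 4 − 5.33·p(drug) + 3.20·p(placebo). It is inflated only if placebo dropout exceeds 5.33 / 3.20 = 1.67 times drug dropout.

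Power comes from simulation: 4,000 runs, SD 7.4, compound symmetry with r = 0.5, and 42 per arm (5%/5%) or 46 per arm (other rows), so that about 80 reach week 9. LOCF with ANCOVA at week 9 was compared with a maximum-likelihood unstructured model on observed data.

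| Dropout drug/placebo | LOCF week 9 difference (true 4.0) | Power, LOCF | Power, observed data |
|---|---|---|---|
| 5%/5% | 4 − 0.267 + 0.160 = 3.89 | 77% | 77% |
| 10%/15% | 4 − 0.533 + 0.480 = 3.95 | 81% | 79% |
| 20%/5% | 4 − 1.067 + 0.160 = 3.09 | 60% | 79% |
| 5%/20% | 4 − 0.267 + 0.640 = 4.37 | 88% | 78% |

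Varying the assumptions: at 20%/5%, s = 0.4 gives 3.21, and halving the placebo slope (1/2/3 against 2.3/4.7/7) gives 3.33. With no placebo improvement, 5%/20% gives 3.89.

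**Step 3: the overall comparison (mean of three visits).** Week 6 under LOCF is (1 − p·s)·m6 + p·s·m3, and week 3 is unaffected. Set the true overall difference to 4.
- Growing separation (drug 4/8/12): loss per unit of dropout is (2.4 + 6.4) / 3 = 2.93 on drug and (1.2 + 3.2) / 3 = 1.47 on placebo. LOCF gives 3.93 (5%/5%), 3.49 (20%/5%) and 4.15 (5%/20%).
- Constant separation (drug 6/8/10): the loss is 1.47 in both arms. LOCF gives 4.00, 3.78 and 4.22.

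**Step 4: no true effect.** With both arms at 2/4/6 and random dropout of 5%/20%, LOCF creates 3.20 × (0.20 − 0.05) = 0.48 points in favour of drug at week 9. Simulated week 9 type I error (LOCF against observed data):
- random dropout, 5%/20%: 6.3% against 4.5% (8,000 runs)
- worse last scores leave more often (logit +1 per SD): 9.2% against 4.0% at 5%/20%; 8.8% against 4.5% at 20%/5%; 4.6% against 4.7% at 5%/5%
- better scores leave more often, 5%/20%: 5.4% against 5.0%
- 20%/20%, with only placebo dropout depending on score: 6.7% against 4.5%, bias 0.57. Equal rates alone do not protect.

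A separate large-sample simulation (400,000 per arm) shows the same pattern. Across its scenarios LOCF shifts the week 9 difference by 0 to about 1.3 points and the overall difference by 0 to about 0.6, in either direction. The likelihood model recovers the true value whether dropout is random or depends on observed scores.

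**Step 5: patients with no post-baseline score.** If baseline is carried forward, the week 9 difference is (1 − q(drug)) × 10 − (1 − q(placebo)) × 6. With 5%/5% such patients it is 9.5 − 5.7 = 3.80; with 5%/0% it is 9.5 − 6 = 3.50.

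**The case against.** Four points deserve an answer.

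- *At the only dropout rate the SAP gives, little happens.* This is true: 3.89 against 4.0, and the same power. With equal random dropout and a constant effect there is no bias at all. Every material effect needs unequal or larger dropout, or dropout that depends on scores differently by arm, and the SAP reports none of these. But the under-5% figure belongs to the original calculation, dropout was then examined at the interim, and the target was restated in completers. Nothing shows that 5% still holds. Recruiting to 80 completers protects power, but those who leave are still filled by LOCF.
- *The power and error rates are for week 9, while 6.2 names the overall comparison.* This stands as a matter of size. In the same set-up tested on the mean of the three visits, when worse scorers leave at 5%/20% under no effect, type I error is 7.2% with bias 0.44, against 10.1% and 0.87 at week 9 in that run. With a constant 4-point effect and 20%/5%, overall power is 94%, against 98% with no dropout. The harm is roughly half or less.
- *The simulations favour the likelihood model, because every dropout mechanism used meets its assumption.* This is also true. They show that LOCF fails where the simpler analysis works, not that the simpler analysis is safe if data are missing not at random.
- *Section 7 was not available to this review.* It could in principle say more, but the sections that govern missing data (9.1 and 10.2) were complete, so it is unlikely to undo the rule.

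**Conclusion.** The concern holds and should be fixed. LOCF is the weaker method here and is unnecessary for any patient with a post-baseline score, but the bias is conditional. It is about 0.1 point at week 9 if dropout stays near 5% and equal. In the hypothetical 20%/5% and 5%/20% cases it is about −0.9 and +0.4 point at week 9 with growing separation, and roughly half that on the overall comparison. With no true effect, week 9 type I error can reach about 9% when dropout is unequal and related to score. The direction cannot be predicted from the document.

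These figures rest on assumed trajectories, dropout timing, SD 7.4 and the reading of 0.27 as Cohen's f. That LOCF is prescribed, and that no alternative analysis of SHAPS is stated in the missing-data and analysis sections, rests on the text itself.

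**What to change.** If the randomisation code is still unbroken:
- In 9.1 and 10.2.1, replace LOCF with the same mixed model fitted by REML to all observed post-baseline scores, and state the missing-at-random assumption. Section 10.2.2 then follows.
- State how patients with no post-baseline score are handled. They add nothing to a model with baseline as covariate, so report their number by arm and include them in the multiple-imputation analysis below.
- Keep LOCF as a labelled sensitivity analysis and say whether baseline may be carried forward.
- Add one analysis for data not missing at random (delta-adjusted or reference-based multiple imputation), and report dropout by arm and visit. These support the main change, which does not depend on them.

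If the code is already broken, keep the planned LOCF result as primary and report the observed-data model as a labelled post hoc sensitivity analysis.

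The cost is a wording change in two sections plus the added sensitivity work; the 74 is unchanged. The standard error rises slightly (1.44 against 1.39 at week 9 with 20%/5%), and at 10%/15% power is about 2 percentage points lower than with LOCF. The change alters the primary analysis after an interim look at the primary outcome. An independent statistician did that look, but the change must be dated and documented, and it may depart from the published protocol, which was not reviewed. Section 10.2.2 already records one change, to the SHAPS remission definition, made before unblinding; the SAP does not show whether the code is still unbroken.
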